5.2. Registry Exclusion Criteria

AMICS patients who meet any of the following study exclusion criteria will have a limited set of data collected via a single-page Patient Exclusion Form completed and submitted within 45 days of hospital discharge, which includes the reason for exclusion, date of index PCI, and assessment of patient survival to hospital discharge:

- 1. Evidence of Anoxic Brain Injury
- 2. Unwitnessed out of hospital cardiac arrest or any cardiac arrest in which return of spontaneous circulation (ROSC) is not achieved within 30 minutes
- 3. IABP placed prior to MCS
- 4. Septic, anaphylactic, hemorrhagic, and neurologic causes of shock
- Non-ischemic causes of shock/hypotension (pulmonary embolism, pneumothorax, myocarditis, tamponade, etc.)
- 6. Active bleeding for which MCS is contraindicated
- 7. Recent major surgery for which MCS is contraindicated
- 8. Mechanical complications of AMI (acute ventricular septal defect (VSD) or acute papillary muscle rupture)
- 9. Known left ventricular thrombus for which MCS is contraindicated

- 10. Mechanical aortic prosthetic valve
- 11. Contraindication to intravenous systemic anticoagulation which precludes placement of MCS.

6. Risks/Benefits of and Alternatives to Patient Participation

This is not a treatment study. This is a single-arm registry that captures data generated during procedures which are considered standard of care using FDA-approved technologies.

There are no risks other than breach of confidentiality. To mitigate this risk, only a limited set of data directly related to the research will be captured, and all data will be stored in a secure REDCap database (please see below).

7. Data Management

Data collected from the participating sites will be securely stored and managed at Henry Ford Hospital in Detroit, Michigan. Electronic data will be stored and managed in a secure REDCap study database hosted through the Henry Ford Health System Department of Public Health Sciences in Detroit, Michigan. REDCap (Research Electronic Data Capture) is a secure, web-based application designed to support data capture for research studies. A study-specific database was created solely for CERAMICS study that includes only the specific data fields that pertain to the data points collected on the case report form (CRF) or Patient Exclusion Form (PEF) (see Appendix 3).

For patients who present to affiliated hospitals with AMICS but are excluded from a CRF (see section 5.2), a Patient Exclusion Form will be submitted to track the reasons for exclusion (see Appendix 3).

The CRFs and Patient Exclusion Forms from an individual site will be transmitted to the lead site, Henry Ford Hospital, via secure email and accessed only on hospital-approved, password-protected computers and stored on a password-protected and encrypted OneDrive system by Microsoft. Access to the OneDrive system and the REDCap database will be managed at Henry Ford Hospital by the NCSI coordinator and the investigators of the study via hospitalapproved, password-protected computers inside locked offices in Henry Ford Hospital.

8. Access to Patient Information

The following will have access to the de-identified patient medical information, and any necessary research contracts and Data Use Agreements will be completed for each participating site.

Henry Ford Hospital – Detroit, Michigan CERAMICS team:

- **Principal Investigators**
- Co-Investigators
- Study Research Coordinator(s)
- Research Nurse(s)
- Research Assistant(s)
- Data Coordinator(s)
- Statistician, based at Henry Ford Hospital

9. Analysis and Publication of Data

There will be planned interim analysis of the data for the purpose of presentations, as well as a final analysis and submission for publication of all data at the end of the study.

Demographics, admission characteristics, procedural characteristics, clinical characteristics, procedural outcomes, in-hospital outcomes, disposition, 30-day survival and 1-year survival will be analyzed. The primary outcome of the study will be to assess mortality in AMICS at study sites with the ability to implant, and if needed, escalate MCS. The CERAMICS study is an observational study and as such prone to bias, confounding and thus causality should not be inferred. However, research in AMICS is difficult to perform and there is significant heterogeneity in care. Thus, even observational data, despite its limitations, can be practice changing and valuable to the care of this high-risk cohort.¹⁰

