Patients presenting with AMICS are critically ill, with >40% of patients presenting in cardiac arrest, patients are frequently sedated, intubated and have cognitive dysfunction. Due to the critical nature and extremes of patients with AMICS, we are requesting a full waiver of informed consent and HIPAA authorization from the IRB for data collection and submission under the guidelines of 45 CFR 46.116(f) and 45 CFR 64.512(i)(2)(ii).

All study data collection is occurring retrospectively at each time-point only using EMR, and there will be no contact between study personnel and patients. Patients will be discharged or deceased at the time of study entry.

Sites seeking to join CERAMICS will need approval from their internal/local/system IRB, or the ability to either directly use WCG IRB or receive approval from their institutional/local/system IRB to defer to WCG IRB as the IRB of record and oversight for the study. For sites choosing to defer study oversight to a national IRB, the study will be reviewed by WCG IRB (formerly known as "WIRB" - Puyallup, WA), an independent IRB with AAHRPP accreditation and ISO 9001 certification for quality management.

All data is being collected via retrospective EMR review only - no patient contact will be made, including screening form, case report form (CRF), and the 30-day and 1-year follow-up forms. A limited data set of PHI will be collected (patient age, date of admission, date of MCS implant/explant, date of discharge/death) for the CRF or exclusion form, but no direct patient identifiers (i.e., name, date of birth, SSN, etc.) other than date of death will be collected. Study data forms will be submitted only after hospital discharge.

3. Research Procedures

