5.1. Inclusion Criteria

AMICS patients who meet the following inclusion criteria, and none of the exclusion criteria, will have a case report form (CRF) completed and submitted within 45 days of hospital discharge:

- Diagnosis of acute myocardial infarction (AMI) with ECG and/or biomarker evidence of S-T elevation myocardial infarction (STEMI) or non-S-T elevation myocardial infarction (NSTEMI).
- 2. Cardiogenic shock is defined as the presence of at least two of the following:
 - a. Hypotension (systolic blood pressure ≤90 mm Hg, or inotropes/vasopressors to maintain systolic blood pressure ≥90 mmHg).

- b. Evidence of end organ hypoperfusion: elevated serum lactate levels (venous or arterial), cool extremities, oliguria/anuria.
- c. Hemodynamic criteria represented by a cardiac index of $< 2.2 \text{ L/min/m}^2$ or a cardiac power output ≤ 0.6 watts.
- 3. Patient is supported with a transvalvular MCS as the initial MCS device.
- 4. Patient undergoes PCI within 12 hours of hospital presentation.

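### Exclusions 1, 2 and 8 have no reference time and are applied once vital status is known, so a fatal arrest on support can, as written, remove a treated patient from the mortality cohort

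*Protocol*

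**What the plan says.** Protocol section 5.2 lists eleven exclusions. Exclusion 2 covers unwitnessed out-of-hospital arrest and, in its second limb, "any cardiac arrest in which return of spontaneous circulation (ROSC) is not achieved within 30 minutes". Exclusion 1 reads "Evidence of Anoxic Brain Injury". Exclusion 8 names "Mechanical complications of AMI (acute ventricular septal defect (VSD) or acute papillary muscle rupture". None of the three says when the condition must have occurred. Exclusion 3 does: "IABP placed prior to MCS".

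Section 5.1 gives the allocation rule. Patients who meet the inclusion criteria (among them a transvalvular device as initial MCS, and PCI within 12 hours) "and none of the exclusion criteria, will have a case report form (CRF) completed". Anyone meeting an exclusion gets a one-page Exclusion Form instead, "which includes the reason for exclusion, date of index PCI, and assessment of patient survival to hospital discharge".

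Section 2 fixes when this is decided: "Patients will be discharged or deceased at the time of study entry". It also lists a limited data set that includes "date of MCS implant/explant, date of discharge/death) for the CRF or exclusion form". Section 9 makes mortality the primary outcome, and section 6 describes a single-arm registry.

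**The concern.** A missing time anchor does little harm when eligibility is settled at enrolment, because later events cannot be seen. Here the person who applies the criteria has the whole hospital record, including any terminal arrest. If exclusion 2 is applied as worded, a patient who received the device and PCI and then died in an unresuscitated arrest on support meets an exclusion and gets no CRF. The way the patient died decides whether the death is counted.

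Exclusions 1 and 8 share the gap, because anoxic injury, septal defect and papillary muscle rupture can all first become evident after implant.

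No control arm shares the selection. The background section says that the registry's interest is escalation and ICU care, which is the period when such events occur. If the 20 sites read the criteria differently, the cohort also differs by site.

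**Working it through.** **1. Which exclusions are anchored.** Exclusion 3 is tied to the time before MCS. Exclusions 4 and 5 concern the cause of the shock. Exclusions 6, 7, 9 and 11 concern whether MCS is contraindicated or precluded. Exclusion 10 (a mechanical aortic valve) is ordinarily a pre-existing condition. That leaves 1, 2 and 8 open-ended. In exclusion 2 the first limb is limited to out-of-hospital arrest, while the second widens to any arrest and so takes in arrests in hospital.

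**2. The chain as written.** Treated with MCS and PCI → arrest on support without ROSC in 30 minutes → death → chart reviewed afterwards (section 2) → exclusion 2 met → no CRF (section 5.1) → not in the mortality cohort. Nothing in these sections breaks the chain.

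**3. Illustration of size.** The protocol gives no rate of such events. The background section reports in-hospital arrest in 27% of patients in the predecessor registry (NCSI), but not when it occurred relative to implant or how long ROSC took. The numbers of removals below are therefore assumptions. The baseline assumes that NCSI rates apply; NCSI's own exclusions are not given.

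Inputs: 73% in stage C/D and 27% in stage E; survival to discharge 79% and 49%; 30-day survival 77% and 46%; n = 120.

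- In-hospital mortality: 0.73 × 0.21 + 0.27 × 0.51 = 0.291, about 35 of 120.
- 30-day mortality: 0.73 × 0.23 + 0.27 × 0.54 = 0.314, about 38 of 120.

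Removing k deaths from D deaths gives (D − k)/(120 − k):

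| Deaths removed | Share of in-hospital deaths | In-hospital mortality | Shift | 30-day mortality |
|---|---|---|---|---|
| 0 | 0 | 35/120 = 29.2% | 0 | 38/120 = 31.7% |
| 1 | 1/35 = 3% | 34/119 = 28.6% | 0.6 points | 37/119 = 31.1% |
| 3 | 3/35 = 9% | 32/117 = 27.4% | 1.8 points | 35/117 = 29.9% |
| 6 | 6/35 = 17% | 29/114 = 25.4% | 3.7 points | 32/114 = 28.1% |

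For scale, the 95% half-width is 1.96 × √(0.292 × 0.708/120) = 0.081, about 8 points.

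**4. Direction.** Exclusion 2 is defined by ROSC not achieved within 30 minutes, not by death. A survivor whose circulation returned later would also be removed. With s such survivors, observed mortality is (35 − k)/(120 − k − s). This lies below 35/120 as long as k/(k + s) exceeds 29.2%, that is, as long as removed patients die more often than the cohort. With k = 3, reversal needs s above 3 × 85/35 = 7.3: seven survivors give 32/110 = 29.1%, eight give 32/109 = 29.4%. Net understatement is therefore likely, but the wording does not guarantee it. The same condition governs exclusions 1 and 8.

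**5. What can be recovered.** The Exclusion Form has the reason and survival to discharge. Section 2 lists implant and death dates for the CRF or the Exclusion Form. If the Exclusion Form carries those dates, treated patients who were excluded can be identified, and an in-hospital death with its date also fixes 30-day and 1-year status. Not listed are the timing of the excluding condition and the later status of excluded patients discharged alive. If 5% to 10% of treated patients were removed at 80% to 90% mortality (assumed), the latter group is 0.05 × 0.10 = 0.5% to 0.10 × 0.20 = 2% of the treated cohort.

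**The case against.** The strongest reply is that the protocol plainly means conditions present before implant. The arrest limb shares a sentence with a presenting feature. Section 4 calls for data on patients who present with shock whether or not they survive the stay. Section 7 speaks of patients who present and are excluded. Section 2 links the Exclusion Form to patients not treated with MCS. A mortality registry that dropped its own arrest deaths would defeat its purpose. The screening and exclusion forms are not shown and may carry the anchor.

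Much of this stands. The context favours a pre-implant reading, but no section states it as a rule for 20 sites. The link to untreated patients is also not consistent: exclusion 3 presupposes that an excluded patient may go on to MCS, and section 2 lists implant dates for either form. Eligibility rules belong in 5.2 even if a form repeats them.

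It also stands that the size is assumed, that most removals look recoverable, and that an add-back analysis is ordinary content for the SAP, so its absence from the protocol is no defect.

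Three stronger readings might be inferred, and the protocol supports none of them:

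- *Bias is certain and can only lower mortality.* It is zero under a uniform pre-implant reading, and removed survivors with late ROSC pull the other way.
- *The shift exceeds the sampling error.* Removing half of all in-hospital deaths would do so, but nothing in the protocol supports a share of that order.
- *Every arrest ongoing at insertion lacks a rule.* NCSI had 9% under active resuscitation at implant, or 0.09 × 120 = 10.8 patients here. Exclusion 2 already has a 30-minute threshold, so only those whose classification against it is unclear need a further rule. That number is unknown.

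**Conclusion.** The point holds as a gap in a stated eligibility rule. Exclusions 1, 2 and 8 lack a reference time, and because eligibility is judged after the outcome is known, following exclusion 2 as worded lets the primary outcome decide cohort membership. It is not a demonstration that the registry's mortality will be biased.

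The likely net effect is understatement. Its size cannot be derived from the protocol. Under the assumed removals it is 0.6 to 3.7 points in hospital, inside the 8-point half-width. Where it arises it is a systematic error, which a larger sample does not reduce. The conclusion rests on the wording of 5.2 and on the timing of chart review, not on the illustrative figures. It would lapse in practice if the unseen forms already state the anchor and all sites apply it. It should be fixed because the correction is cheap and the outcome affected is the primary one.

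**What to change.** - State in 5.2 that exclusions 2 and 8 apply only to events occurring before insertion of the initial MCS device, and that later events do not remove a patient from the CRF cohort.
- Have the sponsor state the reference time for exclusion 1, including how to treat injury from a pre-implant arrest that is recognised only later. A rule based on what was documented by insertion would keep such patients in the cohort. That is debatable, since section 2 notes that these patients are often sedated and intubated, so the choice should be explicit.
- Have the sponsor state how an arrest ongoing at insertion is classified against the 30-minute threshold.
- Add one Exclusion Form item: whether the excluding condition arose before or after insertion. Confirm that the form carries the implant and death dates.
- Report in-hospital mortality also with MCS- and PCI-treated patients excluded under 1, 2 or 8 added back. This uses data that are largely already collected.

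The cost is a few sentences in 5.2, one form item, slightly more chart abstraction and possibly a less favourable mortality figure. If NCSI used unanchored exclusions, which is not stated, comparison with it would also be affected. No patient contact is needed.
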